## DD-CA Protocol

The Dulce Digital-COVID Aware (DD-CA) study will enroll a total of 172 COVID + and – Hispanic patients with type 2 diabetes according to the inclusion and exclusion criteria outlined below. This study compares discharged patients requiring on-going glucose management who receive a proven texting platform with added COVID-related messages versus discharged patients requiring on-going glucose management who do not receive COVID educational messaging using a digital texting platform.

Inclusion criteria:

- Are a patient admitted to a Scripps Mercy Hospital
- Self-identify as Hispanic/Latino
- Are 18 years of age or older
- Speak English or Spanish
- Have type 2 diabetes diagnosis and A1c  $\geq$  7% in the last 30 days
- Have a cellphone that can receive/send text messages

Exclusion criteria:

- Are pregnant
- Are currently participating in another diabetes or COVID-19 related study
- Do not meet all eligibility inclusion criteria

Research staff review automated electronic health record (EHR) reports to identify potentially eligible patients. Once a patient is determined eligible according to EHR-based study criteria, the attending physician is contacted to approve inclusion in the study. If the nursing staff approved and indicate anticipated discharge to home in <24 hours, the patient is asked if he/she is willing to discuss the study with the research staff. Patients interested in the study are approached by a trained bilingual staff member while inpatient. Patients who are deemed eligible to participate in the study are provided with a copy of the consent form and review all content together with the staff member in Spanish or English (depending on potential participant's language preference). Adequate opportunity is provided to the potential participant to consider all options and ask questions; care is taken to ensure that all participants understand the information and that their participation is voluntary.

After consent is obtained and the patient is enrolled to the study, research staff verbally administer the baseline survey, then unveil the group assignment (enclosed in sealed envelopes by the statistician) to the patient: Intervention group (DD-CA + DTS) or Usual Care group (DTS). Each participant is assigned a unique ID number for de-identification purposes.

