2. Diabetes distress, measured using the Diabetes Distress Scale
3. Diabetes self-management behaviors, measured using the Summary of Diabetes Self-Care Activities Survey
4. Patient-reported physical and mental health, measured using the Patient-Reported Outcomes Measurement Information System Global-10 Health Scale (PROMIS)
5. Knowledge and attitudes towards COVID-19 and COVID-19 diagnosis status, measured using the COVID-19 Patient Survey (Phenix toolkit).

The RE-AIM framework will be used to evaluate the success of the DD-CA versus Usual Care in 1) Reaching a representative segment of the population (Reach); 2) Achieving meaningful outcomes through a well-implemented intervention (Efficacy/Implementation); 3) Creating an intervention that can be adopted by and maintained in a real-world environment (Adoption/Maintenance). As part of the process evaluation, participants from both groups are invited to participate in a telephone-based survey to assess patient experiences and satisfaction related to specific aspects of the study (e.g., content of text messages, receiving and responding to text messages, follow-up phone calls from health coach and diabetes educator) at the conclusion of their 6-month participation in the study. After verbal consent is obtained, study staff interview the patient using a survey script that will take approximately 20-25 minutes to complete by telephone.

Study participants will be offered gift cards as an incentive for completing all follow-up assessments. Participants will receive a \$30 gift card for completing the surveys and labs after 90 days and \$40 gift card for completing the surveys and labs after 180 days. The total incentive for each participant who complete all follow-up assessments (at 90 and 180 days) is \$70. In addition, participants will be offered a \$30 gift card for participating in the telephone-based process evaluation survey.

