Our secondary outcomes will be measured through self-report assessments. Baseline patient-reported outcome surveys will be administered immediately after enrollment and prior to randomization. At 90-days, research assistants will obtain the patient-reported outcomes assessment during the follow-up visits and changes from baseline will be compared between groups by  $t$ -tests at each time point. An additional secondary outcome will compare rates between groups of new COVID-19 infections over the 90-day follow-up window via the COVID-19 Patient Survey. Differences in proportions of patients experiencing new infections per group will be compared by Fisher's exact tests. Similar to our primary outcome, we will also examine differences in 90-day hospital readmissions between groups. Unadjusted between-group differences will first be analyzed by comparing proportion of patients with any hospital readmissions within the 90-day period by a Fisher's exact test.

Process outcomes to be assessed following the RE-AIM evaluation framework, and quantitative outcomes will be assessed as follows: To examine enrollment rate, EMR-derived demographic and characteristics of eligible patients will be compared between those who enroll versus decline; where continuous measures will be compared between groups by student's  $t$ -tests and categorical measures will be compared between groups by Chi-Square tests. To examine generalizability of our sample, distribution of demographics in our sample will be compared to expected distributions of our target population through Chi-square tests. Results of semi-structured interviews will be descriptively analyzed to reveal perceptions of implementation efficacy, challenges, satisfaction, and benefits. Physicians' pre- and post-study perceptions and knowledge of, and identified barriers to successful implementation of a

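### The enrolment-rate analysis compares enrollees only with decliners, omitting EHR-eligible patients who are never asked, so it cannot by itself support the Reach objective

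*Combined protocol and SAP*

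**What the plan says.** The DD-CA Protocol lists three RE-AIM aims, the first being "Reaching a representative segment of the population (Reach").

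For enrolment rate, the Statistical Analysis Plan names one analysis with two groups: "EMR-derived demographic and characteristics of eligible patients will be compared between those who enroll versus decline", using t-tests and chi-square tests. It gives no formula or denominator for the rate itself. A second analysis addresses generalisability: "distribution of demographics in our sample will be compared to expected distributions of our target population through Chi-square tests". The target population is not defined.

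The recruitment text in the DD-CA Protocol sets out the order of events. First, "Once a patient is determined eligible according to EHR-based study criteria, the attending physician is contacted to approve inclusion in the study". Then comes the invitation, under further conditions: "If the nursing staff approved and indicate anticipated discharge to home in <24 hours, the patient is asked if he/she is willing to discuss". Only after that can a patient accept or refuse.

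**The concern.** Physician approval, nursing approval and expected discharge home all come after EHR eligibility, and none is in the listed inclusion or exclusion criteria. A patient stopped at one of them can therefore be eligible by the protocol's own list, yet has neither enrolled nor declined. The SAP comparison has no place for that patient.

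Enrollees and decliners have both passed the clinicians and the discharge condition. Comparing them tests whether patients' own refusal was selective. It cannot test whether selection before the invitation was. If the two groups look alike, the report could be read as evidence of representative reach when the comparison does not bear on that step. The Reach conclusion, and any claim about where the programme could be adopted, would then rest on an incomplete comparison.

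**Working it through.** **The plan's own figures.** The documents state no enrolment rate and no screening counts, so there is no Reach figure to reproduce. The only computable figure is the sample size. A one-sided Fisher's exact test of 40% versus 20% at alpha 0.05 needs 73 per arm (exact power 0.803), 146 in all, and 146/0.85 = 172. It reproduces and does not bear on this point.

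**Who is in the comparison.**

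- Meets EHR criteria, physician or nurse does not approve: in neither group.
- Meets EHR criteria, never expected to go home, or leaves before being approached: in neither group.
- Asked and refuses: decline group.
- Asked and consents: enrol group.

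**Effect on the comparison of characteristics.** Let g be the share of EHR-eligible patients never asked. Suppose enrollees and decliners have the same mean m on some EMR variable, and patients not asked have mean m + δ.

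- Enrolled minus declined = 0, whatever δ is.
- Mean of all eligible patients = (1 − g)m + g(m + δ) = m + gδ.
- Enrolled minus all eligible = −gδ.

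The planned comparison is blind to −gδ. The documents give neither g nor the sign of δ, so the direction is unknown.

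**Effect on the rate, if it is computed from the two named groups.** Let E be enrolled, D declined and G not asked.

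- Rate among those asked: r = E/(E + D).
- Rate among all EHR-eligible: E/(E + D + G) = r(1 − g).
- Overstatement: 1/(1 − g).

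With E = 172 from the protocol, and with r and g assumed:

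| Assumed r (number asked) | g = 0 | 10% | 20% | 30% | 50% |
|---|---|---|---|---|---|
| 50% (344) | 50% | 45% | 40% | 35% | 25% |
| 70% (246) | 70% | 63% | 56% | 49% | 35% |
| 90% (191) | 90% | 81% | 72% | 63% | 45% |
| Overstatement factor | 1.00 | 1.11 | 1.25 | 1.43 | 2.00 |

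For example, at r = 70% and g = 20%, 246 are asked, 246 − 172 = 74 decline and 61 are not asked. Of the 74 + 61 = 135 eligible patients who do not enrol, 61 (45%) would enter no comparison. At g = 0 nothing is lost.

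**What the second check covers.** Comparing the sample with a target population can show demographic under-representation whatever step caused it. It does not cover clinical characteristics and cannot say at which step patients were lost.

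**The case against.** The strongest reply is that the SAP never says the rate is enrolled/(enrolled + declined). If the denominator is all EHR-eligible patients, nothing is overstated. That stands: the factors above are conditional. It does not rescue the comparison of characteristics, whose two groups are written down.

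A reader might infer that patients who are not asked vanish from Reach altogether. The documents do not support that, because the target-population check could reveal demographic gaps. A reader might also infer that the screening steps remove sicker patients, so that Reach is bound to look better than it is. Nothing in the documents says whom clinicians would hold back, and the bias in characteristics could go either way.

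The 24-hour condition may be a timing trigger, since a patient not yet near discharge can qualify later. That is fair, and it means patients should be counted by final status. Patients not going home may also lie outside the intended population of a post-discharge programme. That is arguable, and recording them under their own reason lets either view be reported.

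The protocol uses eligibility in two senses: on EHR criteria, and later for those given the consent form. If the SAP means the later sense, enrol versus decline covers nearly everyone in that group. But that group has already been through clinician selection, so the gap with the Reach aim remains.

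Finally, it is tempting to count the phone requirement, "Have a cellphone that can receive/send text messages", as part of the same loss. It is a stated inclusion criterion for a texting intervention. Patients failing it are ineligible and should be counted separately, not as eligible patients who were not asked.

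**Conclusion.** The point holds in a limited form. The two-group comparison omits EHR-eligible patients stopped before being asked, so similarity of enrollees and decliners cannot by itself support a claim of representative reach. This follows from setting the recruitment text beside the SAP and needs no assumption beyond some patients being stopped.

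The size is not known. If the rate were enrolled/(enrolled + declined), the overstatement would run from none at g = 0 to a factor of 2.0 at g = 50%, and g is not in the documents. An inflated enrolment rate, or a Reach result biased towards success, is therefore a possibility and not a finding.

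The matter is confined to a process outcome with no stated success threshold. The randomised readmission comparison and N = 172 are unaffected. It is worth correcting because the correction is cheap and uses EHR reports and EMR variables already planned for.

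**What to change.** In the RE-AIM paragraph of the Statistical Analysis Plan:

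1. Define the enrolment-rate denominator as all patients meeting the EHR-based criteria, less those later found ineligible (for example pregnant, in another study, or without a texting phone). Report the ineligible separately, with counts.
2. Classify every remaining patient as enrolled, declined or not asked. For those not asked, record the reason: physician or nurse did not approve, not expected to go home, or discharged before approach. Count each patient once, by final status at discharge.
3. Compare EMR characteristics of enrolled patients with all eligible patients not enrolled, keeping enrolled versus declined as a sub-comparison.
4. Report the rate among those asked alongside the rate on the full denominator. Some patients who were not asked may have been ineligible for reasons the EHR does not hold; the rate among the truly eligible then lies between the two.

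The cost is recording reasons during screening (the documents describe no screening log, so this may be new work), any approval needed to use EMR data of patients who were not asked, and a possibly lower reported enrolment rate.

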## Statistical Analysis Plan

The statistical software G\*Power was used to estimate the sample size needed to detect differences between groups (DD-CA vs. Usual Care) for the primary outcome, rate of readmission within 30 days post discharge in the proposed randomized-controlled trial. From a pilot study in a similar population, we determined that an absolute reduction of 20% of patients readmitted within 30 days between the two groups would be clinically meaningful based on an estimated 40% readmissions rate within 30-days in the UC arm. Participants will be 1:1 randomized between the study arms, and group assignments will be determined by a random number generator and provided in sealed envelopes to prevent selection bias. Additional assumptions include one-sided alpha = 0.05, and power = 0.80. We estimate maximum of 15% of participants being excluded from analyses due to loss to follow up or request to withdraw. Given these assumptions,  $N = 172$  participants are needed to detect a difference in readmission rates of this magnitude between study arms by a Fisher's Exact test.

The statistical software R and SPSS will be used for all analyses. Patient-reported indicators and clinical will be compared between groups to assess randomization among study arms by Chi-squared tests of proportions to compare categorical variables and student's  $t$ -tests to compare continuous variables. For our first aim we will compare rates of readmissions between the DD-CA and Usual Care groups within 30 days of discharge following study enrollment. The electronic medical records will be used to identify admissions for any patients in the study during each patient's unique follow up period. Unadjusted between-group differences will be analyzed by comparing proportion of patients with any hospital readmissions within the 30-day period by a Fisher's exact test.. For our second aim we will compare glycemic control between groups through HbA1c measurements captured for each study participant 90-days post discharge. Unadjusted group mean differences in HbA1c at each of the two timepoints will be assessed with a student's  $t$ -test.

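### Student's equal-variance t-test is named for enrolled versus declining patients, where nothing in the plan makes group sizes or spreads equal; Welch's test is a safer choice at little cost

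*Combined protocol and SAP*

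**What the plan says.** The process-outcome paragraph of the Statistical Analysis Plan examines enrollment using data from the medical record: "characteristics of eligible patients will be compared between those who enroll versus decline". For the method it adds: "where continuous measures will be compared between groups by student's" t-tests, with Chi-square tests for categorical measures. It mentions no unequal-variance version and no check of variances.

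The DD-CA Protocol section says the study "will enroll a total of 172 COVID" positive and negative patients, so one side of this comparison is planned at 172. No number of decliners is given, and no SD for any of the measures. The 1:1 allocation applies only to the two trial arms. The one significance level in the plan, "one-sided alpha = 0.05, and power = 0.80", belongs to the sample size for the primary outcome; none is stated for this comparison.

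**The concern.** Student's test pools the two sample variances. With equal group sizes, pooling does little harm even if the spreads differ, and 1:1 randomisation gives the trial arms that protection. Enrolled and declining patients do not have it. Patients choose their own group, one group is planned at 172, and the other is whatever recruitment yields. Self-selection can change the spread of a measure as well as its mean.

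If sizes and spreads both differ, the error has a known direction. When the smaller group is the more variable, the test rejects too often; when the larger group is the more variable, it rejects too rarely. Which case applies cannot be known when the plan is written.

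The comparison is part of the evidence on Reach, one of the RE-AIM criteria in the protocol. A test that rejects too rarely could hide a real difference in mean age or HbA1c between those who join and those who decline. A test that rejects too often could signal a difference in means that is not there.

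**Working it through.** **The plan's own figure.** The documents give no figure for this comparison. The only stated number that enters is N = 172, and it reproduces. For a one-sided Fisher's exact test of 40% versus 20% at alpha 0.05, exact power is 0.797 with 72 per arm and 0.803 with 73. That makes 2 × 73 = 146 analysed, and 146 / 0.85 = 171.8, rounded up to 172.

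**Inputs.**
- Enrolled, n1 = 172: DD-CA Protocol section.
- Decliners, n2: not given; assumed 40 to 350.
- SD ratio r (decliners / enrolled): not given; assumed 0.67 to 1.5, with the enrolled SD set to 1.
- Level: not given for this comparison; two-sided 5% assumed.

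**Formula.** With no true difference in means:
- Pooled variance (expected): s² = [(n1 − 1) + (n2 − 1)r²] / (n1 + n2 − 2)
- Variance the test assumes for the difference: A = s²(1/n1 + 1/n2)
- True variance of the difference: T = 1/n1 + r²/n2
- Type I error ≈ 2Φ(−1.96c), where c = √(A/T)

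If n1 = n2 then A = T (apart from sampling error) for any r. If r = 1 then A = T for any n2. Either condition alone brings the error back to 5%.

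**Worked cases.**
- 40 decliners, r = 1.5: s² = (171 + 39 × 2.25)/210 = 1.232; A = 1.232 × 0.03081 = 0.03797; T = 0.00581 + 0.05625 = 0.06206; c = 0.782; error = 2Φ(−1.533) = 12.5%.
- 40 decliners, r = 0.67: s² = (171 + 39 × 0.4489)/210 = 0.898; A = 0.02766; T = 0.00581 + 0.01122 = 0.01704; c = 1.274; error = 2Φ(−2.497) = 1.3%.
- 350 decliners, r = 0.67: s² = (171 + 349 × 0.4489)/520 = 0.630; A = 0.005464; T = 0.00581 + 0.00128 = 0.00710; c = 0.877; error = 2Φ(−1.720) = 8.5%.

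**Type I error of Student's test from the formula, nominal 5%.**

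| Decliners | r = 0.67 | 0.9 | 1.1 | 1.25 | 1.5 |
|---|---|---|---|---|---|
| 40 | 1.3% | 3.6% | 6.5% | 8.8% | 12.5% |
| 60 | 1.8% | 3.9% | 6.1% | 7.8% | 10.5% |
| 100 | 3.0% | 4.4% | 5.6% | 6.4% | 7.7% |
| 172 | 5.0% | 5.0% | 5.0% | 5.0% | 5.0% |
| 350 | 8.5% | 5.9% | 4.3% | 3.5% | 2.5% |

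**Simulation check** (normal data, 40,000 data sets per cell). At r = 0.67 and r = 1.5, Student's test gave 1.3% and 12.2% with 40 decliners, 1.8% and 10.3% with 60, 2.9% and 7.7% with 100, and 8.8% and 2.6% with 350. Welch's test stayed between 4.8% and 5.3% in these cases.

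**Randomised arms.** With 73 per arm and an SD ratio of 1.5, both tests were at 5.0%.

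**Cost of Welch's test.** Power was simulated with equal SDs and a true difference of 2.8 standard errors:

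| Decliners | Student | Welch |
|---|---|---|
| 20 | 79.4% | 76.5% |
| 40 | 79.7% | 78.7% |
| 57 | 79.3% | 79.0% |
| 86 | 79.4% | 79.3% |

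**The case against.** The strongest reply is that the harm needs two conditions and the documents establish neither. A reader might infer that the two groups are known to be of unequal size. They are not: 172 is planned on one side and nothing is said about the other, and about 172 decliners would remove the problem. Unequal spread is also an assumption. Both groups come from patients meeting the same eligibility criteria, and nothing in the documents points to an SD ratio as far from 1 as 1.5 or 0.67. Near 1 the distortion is modest. This stands, and it makes the point conditional.

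A reader might also infer that the error depends only on how many patients decline. It does not: with equal spreads the test is correct at any number. Nor is the change free, since Welch's test loses some power when decliners are few and SDs are equal.

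It can further be said that groups with clearly different spreads do differ in composition, so a rejection is not wholly false. That is fair as far as it goes. The inflated error concerns equality of means only, but that is what a t-test is read as testing, and the opposite error, a masked difference in means, remains.

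Finally, this is a process comparison with no stated significance level or decision rule. Categorical characteristics and generalizability have their own Chi-square tests, so Reach does not rest on this test alone. That limits the importance of the point. It does not make the pooled test the better choice.

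**Conclusion.** The point holds as a minor, conditional improvement. The plan names a test whose error rate is reliable only if sizes or spreads are about equal, and it applies that test to two self-selected groups for which it secures neither. Under the assumed 40 to 350 decliners and SD ratios of 0.67 to 1.5, type I error lies between about 1% and 12%. At SD ratios of 0.9 to 1.1 it lies between about 3.5% and 6.5%. These ranges rest on normal data and a two-sided 5% level as well as on the assumed counts and ratios.

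A reader might extend this to the plan's other Student's t-tests. For the tests between randomised arms the documents do not support that, because 1:1 allocation keeps the sizes close to equal. The primary analysis is a Fisher's exact test, so neither it nor N = 172 is touched.

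**What to change.** In the process-outcome paragraph of the Statistical Analysis Plan, name Welch's unequal-variance t-test for continuous measures in enrolled versus declining patients. Report each mean difference with its Welch 95% confidence interval. Make the choice in advance rather than after looking at the variances. The tests between randomised arms need no change for this reason.

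The cost is a few words in the plan. The data are the same, and both planned packages, R and SPSS, compute the test. The statistical price is the power loss shown above when SDs are equal: about 3 points with 20 decliners, about 1 point with 40, and next to nothing from about 60 upward.

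### Generalisability rests on chi-square tests against the target population, which can show neither similarity nor the size of a departure; report differences with 95% intervals instead

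*Combined protocol and SAP*

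**What the plan says.** The DD-CA Protocol section lists the RE-AIM criteria by which the programme will be evaluated against usual care. The first is "Reaching a representative segment of the population (Reach").

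The process-outcomes paragraph of the Statistical Analysis Plan gives the method. "To examine generalizability of our sample", the "distribution of demographics in our sample will be compared to expected distributions of our target population through Chi-square tests". Just before that, it describes a companion analysis of enrolment in which "characteristics of eligible patients will be compared between those who enroll versus decline", by t-tests and chi-square tests.

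For the comparison with the target population, the documents give no significance level, effect measure, interval or margin. They name neither the demographic variables nor the source of the expected distributions. The sample size was set for 30-day readmission alone: 172 "participants are needed to detect a difference in readmission rates of this magnitude between study arms by a Fisher's Exact test".

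**The concern.** The Reach question is how closely the enrolled patients resemble the target population. A chi-square test answers a different question, namely whether the data contradict an exact match. A large p-value may mean a close match or too few patients to see a mismatch. A small p-value shows that some mismatch exists, but not whether it is large enough to matter or in which direction it runs.

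The p-value is the only output planned for this comparison, so a reader of the results would have little else to go on. The trial addresses barriers in underserved Hispanic communities, and the size and direction of any under-representation is the useful result. The planned method does not report it.

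**Working it through.** **The plan's own figure.** The documents state N = 172 for the primary outcome, from 40% versus 20% readmitted, one-sided alpha 0.05, power 0.80, 1:1 allocation, Fisher's exact test and 15% exclusions. By exact enumeration, 73 per arm is the first size to reach the target (power 0.803). Then 2 × 73 = 146, and 146 / 0.85 = 171.8, which rounds up to 172. The figure reproduces, but it says nothing about the generalisability comparison.

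**Inputs for this check.** n = 172 is the planned enrolment. Assumed, because the documents do not give them: a two-sided 0.05 level, a two-category variable, target shares p0 of 20% to 50%, and baseline demographics from all 172 patients.

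**Formula.** With x patients in the category, X² = (x − n·p0)² / (n·p0·(1 − p0)), and the test rejects when X² > 3.84. At p0 = 0.50 this is (x − 86)² / 43. It rejects when |x − 86| > √(3.84 × 43) = 12.8, that is for x ≤ 73 or x ≥ 99. Power is the binomial probability of that region under the true share.

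**Power by exact binomial, upward / downward shift:**

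| Target share | 5-point shift | 10-point shift |
|---|---|---|
| 50% | 27.6% / 27.6% | 76.8% / 76.8% |
| 40% | 26.5% / 27.9% | 75.4% / 79.4% |
| 30% | 29.7% / 27.2% | 79.5% / 83.5% |
| 20% | 39.1% / 40.0% | 88.2% / 96.3% |

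A 5-point shift is therefore missed about 60% to 73% of the time, and a 10-point shift is detected about 75% to 96% of the time.

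**Where misses become more likely than not.** For one degree of freedom and n = 172, power is 50% at effect size w = 0.149, and the shift is w·√(p0(1 − p0)):
- 50% share: 0.149 × 0.500 = 7.5 points
- 30% share: 0.149 × 0.458 = 6.8 points
- 20% share: 0.149 × 0.400 = 6.0 points

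**Fewer patients.** If only 146 contributed, power at a 50% share would be 24% for 5 points and 70% for 10 points.

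**What an interval adds.** The 95% half-width is 1.96·√(p(1 − p)/172), which is 7.5 points at a share of 50% and 6.0 points at 20%. Suppose the target is 50% and 77 of 172 patients (44.8%) are in the category. Then X² = (77 − 86)² / 43 = 1.88, p = 0.17. The difference is −5.2 points, with half-width 1.96·√(0.448 × 0.552 / 172) = 7.4 points, so the interval runs from −12.7 to +2.2. The p-value alone could pass for reassurance. The interval shows that a deficit of more than 10 points has not been excluded.

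**The case against.** The strongest objection is that the plan attaches no decision rule to these tests. It says the comparison will examine generalisability, and nowhere that a non-significant result means the sample is representative. A reader might infer such a rule, but the documents do not contain it. This stands: the risk is a misreading that the plan leaves open, not an error it commits to.

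A reader might also infer that real demographic shifts would usually be missed. That is too broad. It holds only for shifts below about 6 to 7.5 points at the shares considered. Shifts of 10 points are mostly detected.

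Two further inferences lack support. One is that the sample forms part of its own reference list, which would make the test too conservative. The source of the expected distributions is not stated, and the comparison of eligible patients who enrol or decline is described separately. The other is a specific false-alarm rate across many tests, which needs a number of variables that the documents do not give.

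Finally, this is one process outcome among several, and the observed distributions can still be tabulated at reporting. That limits the consequence. It does not make the chi-square test a measure of similarity.

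**Conclusion.** The concern holds in a limited form. The planned method does not match the Reach goal, because a difference test shows neither similarity nor the size of a departure. With 172 patients, modest shifts of about 5 points would mostly go undetected, while shifts of 10 points would mostly be found. These figures rest on the assumed 0.05 level, two-category variables and target shares of 20% to 50%.

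The documents do not support the stronger statements that non-significance will be taken as representativeness, or that shifts of any size are usually missed. The primary and secondary efficacy analyses and the sample size are unaffected. This is a low-priority improvement in reporting.

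**What to change.** In the process-outcomes paragraph of the Statistical Analysis Plan:

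1. Name the demographic variables and the source of the expected distributions.
2. Make the main Reach result the sample-minus-target difference for each demographic category, with its 95% interval. If the reference list contains the sample, multiply the standard error by √(1 − f), where f is the fraction of the list enrolled.
3. Keep any chi-square p-value as supplementary, and state that non-significance is not evidence of representativeness.
4. If representativeness is to be formally claimed, prespecify a margin scaled to each category's target share.

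A flat 10-point margin is tempting but should not be used:
- **It is too lax for small categories.** If a subgroup makes up 5% of the target and none of the 172 patients belong to it, the difference is −5 points and the exact upper 95% limit for the sample share is 1 − 0.025^(1/172) = 2.1%. The interval excludes a 10-point difference, so the subgroup's complete absence would count as representative. The planned chi-square would flag it: 172 × 0.05 / 0.95 = 9.05, p = 0.003.
- **It is too strict for balanced ones.** At a 50% share, a perfectly representative sample would pass only about 51% of the time.

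The cost is a wording change, using the same data. The downside is that some characteristics will be reported as inconclusive, since the half-width is about 7.5 points at a 50% share without the correction.
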